#### IX. Regression models: Planned per protocol analyses

- a. For planned per protocol analyses, we will consider the following analyses for the primary outcome raw change in SDMT (or corresponding measures of processing speed)
- b. Overview of planned per-protocol analyses

- i. Adjusted analyses for additional covariates including DXA-derived body fat, bone density, lean mass, BMI, HOMA-IR
- ii. Stratified analyses by pre-shutdown and shutdown/post-shutdown.
  - 1. Pre-shutdown will be considered as all study visits occurring before March 13, 2020, shutdown will be considered from after March 13, 2020.
- iii. Analyses including excluding any screening SDMT for those missing the baseline SDMT.
- iv. Stratified analyses by key covariates of interest; these will be tested using an interaction term.
  - 1. Disability status (EDSS< median, EDSS≥median), history of depression, number of non-MS medications (<5, ≥5), MS subtype (RRMS, progressive), DMT (yes, no)
- v. Assessing predictors of drop-out/early censoring
  - 1. Baseline covariates will be used to assess whether certain characteristics were associated with follow-up time.

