for eligibility, even if they haven't had a recent clinic visit. For MS Center patients that have not taken an SDMT or PST test, we will use an oral consent process to administer the SDMT test and determine eligibility. SDMT or PST test results obtained within 3 months of the baseline visit will be considered as proof of eligibility for the study and may be screened in person or by phone. The study coordinator will only approach MS Center patients of physicians on the study team or those referred by their treating physician. In addition to the above recruitment strategies, we will obtain home-based PST screening test for our MS patients that have iPADs (Air, Air 2, and iPAD 2017), as the PST app is now available. This will allow for remotely screening potential subjects that have transportation and/or mobility limitations. If at any time point, enrollment is less than 85% of the target, we will interview subjects who have declined to participate to determine the deterrents to enrollment; we will then implement alterations in recruitment needed to enhance enrollment.

Study Treatment: Intranasal insulin (Novolin R, Novo Nordisk, Princeton, NJ) will be evaluated in two doses (10 IU twice a day, 20 IU twice a day) and compared to the sterile diluent (Eli Lilly and Company – NDC:00002-0800) (1:1:1 randomization, stratified by relapsing versus progressive MS). The 20 IU dose will consist of insulin. The 10 IU dose will be a diluted mixture comprised of normal saline and insulin. The study drug, insulin, has a distinct smell. In order to preserve study blinding, we will use the Lilly sterile diluent, which has a similar odor as the insulin, to preserve blinding. The study drug and placebo (Lilly diluent) will be prepared by the Johns Hopkins Investigational Drug Service and will appear identical to maintain blinding. A nasal drug delivery device (Kurve Technology, Lynnwood, WA) will be utilized to ensure optimal exposure of the olfactory epithelium. The treatment regimen was chosen to match that of a recent successful pilot study in Alzheimer's Disease.³⁴ Evaluating two doses will allow for the possibility that any benefit of insulin may be non-linear.

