Aim 3. For the biomarker outcomes, to evaluate variability in the estimated means across groups, assuming that the within-group means are normally distributed, a one-way ANOVA will be conducted at the follow-up visits during the active treatment phase. If the within-group data are strongly non-Gaussian, a Kruskal-Wallis test will be used. A mixed effects longitudinal model will also be used to test if differences across groups exist at follow-up visits. For within-person changes in measures at follow-up compared to baseline or before versus after calorie restriction days, paired t-tests will be used. Correlations between the biomarkers will be assessed. A bootstrap of subjects will be used to obtain 95% equal confidence intervals for these measures. We will also evaluate the biomarker changes after study therapy ends.

Sample Size and Power: Sample size estimates are difficult given the novelty of the project but are based on the goal of detecting a benefit of insulin on cognition. In a pivotal study of two doses of intranasal insulin versus placebo in participants with mild cognitive impairment or mild to moderate Alzheimer's Disease, the Dementia Severity Rating Scale score improved over the four-month treatment course in those receiving intranasal insulin.³⁴ Using the scores in the 10 IU twice a day group, given a two-sided alpha of 0.05 and beta 0.20 (80% power), assuming 3 follow-up cognitive tests and a correlation between baseline and follow-up results of 0.5, 29 subjects per group are required. To account for drop-outs and for the three-arm design, a total of 35 subjects per group is planned. With SDMT as the outcome, for a two-arm design, this sample size confers 80% power (assuming SDMT standard deviation of 9 points and two-sided alpha of 0.05) to detect a 6-point improvement in SDMT which seems reasonable considering that transcranial stimulation with cognitive training

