## VIII. Regression models: Modified intention to treat analyses

- a. Analyses will adjust for age, sex, and years of education. We will also incorporate variables with differences between the treatment arms that exceed 10% as identified using results of the descriptive analyses.
- b. For analytic models for each outcome, the primary hypothesis test will compare INI (regardless of dose) versus PLAC and will be conducted first. Secondary pairwise tests comparing LDINI versus PLAC, HDINI versus PLAC, HDINI will then be conducted.
- c. Analyses will first be conducted first through the week 24 measure (0, 6, 12, 24). Secondary analyses will include weeks 36 and 48 (0, 6, 12, 24, 36, 48) to evaluate a potential sustained effect post cessation of treatment.
  - i. The week 24 visit must have occurred within 25 weeks (i.e., the protocol outlines a 1 week visit window).
- d. Eligible participants for the primary analysis are those with baseline or screening SDMT data
- e. Missing values for key baseline covariates of interest is expected to be small; however, primary analyses will include a missing indicator level for the categorical variable if it is included in analytic models.

- f. For mixed effects models, time will be considered as a linear variable in primary analyses.
  - i. Sensitivity analyses will evaluate potential non-linearity in changes over time using appropriate methods (e.g., quadratic terms for time or splines).
- g. Primary outcome: change in SDMT using raw scores over time
  - i. Change in the raw SDMT score over time will be assessed using a linear mixed effects model with unstructured covariance structure, random intercepts. If model fit is improved with the addition of random slopes, they will be added. The term of interest will be the coefficient for the cross-product term between INI and time.
- h. Secondary outcomes
  - i. Adverse events
  - ii. Change from baseline cognitive function in the tests listed below.
    - Rate of change in each cognitive test will be assessed using a linear mixed effects model with unstructured covariance structure, random intercepts. If model fit is improved with the addition of random slopes, they will be added. The term of interest will be the coefficient for the cross-product term between INI and time.
  - iii. Change in multiple sclerosis (MS) functional composite (MSFC)

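### EDSS and medication count are tested as effect modifiers only as two-level variables, which would further weaken an already weak interaction test if modification is roughly linear

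*SAP*

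**What the plan says.** SAP section IX is confined to the SDMT outcome: "we will consider the following analyses for the primary outcome raw change in SDMT (or corresponding measures of processing speed". Item b.iv then plans "Stratified analyses by key covariates of interest; these will be tested using an interaction term". Five modifiers follow. Three are categorical: history of depression, MS subtype, and use of disease-modifying therapy. The other two are graded but appear only as two groups: "Disability status (EDSS< median, EDSS≥median), history of depression, number of non-MS medications (<5, ≥5".

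The SAP does not write the interaction out. In the main SDMT model (VIII.g), "The term of interest will be the coefficient for the cross-product term between INI and time", so the natural reading is a modifier × INI × time term. The leading contrast pools the doses: "the primary hypothesis test will compare INI (regardless of dose) versus PLAC and will be conducted first" (VIII.b).

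No continuous test of EDSS or medication count is planned, neither cut is justified, and no power is stated for any interaction. SAP V.b.i lists the EDSS score among the baseline characteristics, and a medication count is numeric by nature, so the finer values will be available.

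**The concern.** Splitting a graded modifier treats everyone on one side of the cut as alike. If the treatment effect changes gradually with EDSS or with medication count, the variation within each group is discarded and the interaction test loses power. An interaction test in a trial of 105 has little power to lose.

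The EDSS cut also depends on who enrols. EDSS moves in steps, and all ties at the median go to the upper group, so the two groups may be unequal. An effect contrast tied to this sample's median carries over to another population less readily than a slope per EDSS point.

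At stake is the informativeness of two supportive analyses.

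**Working it through.** **Inputs.** Protocol, Sample Size and Power: "a total of 35 subjects per group is planned", with "80% power (assuming SDMT standard deviation of 9 points and two-sided alpha of 0.05) to detect a 6-point improvement in SDMT". Protocol, Study Treatment: "1:1:1 randomization, stratified by relapsing versus progressive MS". SAP VIII.b: doses pooled, hence 70 versus 35 if everyone is analysed.

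**The plan's own figure.** SE = 9 × √(2/35) = 2.15. Power = Φ(6/2.15 − 1.96) = 79.6% (78.5% with a t-test). The stated 80% is reproduced.

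**Strength of the interaction test.** For a modifier that splits the sample into shares q and 1 − q, the SE of the difference in treatment effect is 9 × √[(1/35 + 1/70) × (1/q + 1/(1 − q))].

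- Equal halves: 9 × √(0.04286 × 4) = 3.73. Power for a 6-point difference is Φ(6/3.73 − 1.96) = 36%. The difference detectable with 80% power is 2.80 × 3.73 = 10.4 points.
- 30/70 split: SE 4.07, power 31%.
- Pooled main effect, for comparison: SE = 9 × √0.04286 = 1.86, detectable difference 5.2 points.

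These figures use a single-visit SD, full retention and no baseline adjustment. The mixed model would change absolute power, but the relative loss from splitting would stay about the same.

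**Information kept by a split.** If the effect changes linearly with the modifier, the share kept is the squared correlation between the modifier and its 0/1 version. For a normal modifier this is φ(c)²/[q(1 − q)], where c is the cut. For a uniform one it is 3q(1 − q). The distributions below are assumed; the documents give none.

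| Modifier and assumed shape | Information lost |
|---|---|
| EDSS at median, uniform | 25% |
| EDSS at median, normal (1 − 2/π) | 36% |
| EDSS steps, ties upward: bimodal | 23% |
| EDSS steps, ties upward: flat | 25–27% |
| EDSS steps, ties upward: bell-shaped | 36% |
| EDSS steps, ties upward: right-skewed | 44% |
| Count at 5, Poisson, mean 2 to 8 | 35–71%, lowest near mean 4 |
| Count at 5, negative binomial (k = 2), mean 2 to 8 | 35–57% |

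The cut at 5 is a fixed number, not a median, so its cost depends on where it falls. For a normal modifier the loss is 38% at a 40/60 split, 42% at 30/70, 51% at 20/80 and 66% at 10/90.

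**Effect on power.** Take a linear modification that produces a 6-point difference between the two halves. The split test has a standardised effect of 6/3.73 = 1.61 and 36% power. The continuous test has about 1.61/√0.75 = 1.86 (uniform) or 1.61/√0.637 = 2.02 (normal), which gives power of about 46% or 52%.

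With a larger assumed modification of 5 SDMT points per SD of the modifier, power is 77% continuous, against 64% (uniform) or 57% (normal) after a median split. A simulation with a normal modifier gave 73% against 53%.

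**The case against.** **The loss is conditional.** It assumes linear modification, and nothing in the documents supports a linear gradient in EDSS, which is an ordinal scale. If modification were a step exactly at the cut, the split would lose nothing. A linear term would then be the weaker test, keeping only 64% for a normal modifier split at its median. This stands, and it is why the loss is given as a range under stated assumptions.

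**Sample size is the real limit.** Five points per SD means a 10-point difference in effect between participants 1 SD below and 1 SD above the mean, more than the 6 points used for sizing. At 2.5 points per SD, with SE 1.86, power is about 27% continuous and 19% split. Neither is informative. This also stands; the gain is real but modest.

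**Prespecification.** The median rule and the handling of ties are set in advance, use a baseline variable and do not depend on outcome. They limit analyst discretion, and no bias is shown.

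**Stronger readings that the documents do not support.** A reader might apply the EDSS loss to medication count, or multiply it into one effective sample size for both tests. The fixed cut at 5 does not behave like a median split, so neither step is sound. A reader might also infer that later trials cannot use these cut-points. In fact 5 is a fixed number, and an observed EDSS median can be reported and copied. Nor is the pilot's stated purpose undermined: the protocol says it will inform phase III through the mean and SD of change in cognitive tests, and promises no effect-modifier estimates.

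**Conclusion.** The concern holds as a cheap improvement to supportive analyses. It affects two of the five listed modifiers. The primary INI × time test is untouched, and the protocol does not expect conclusive efficacy evidence from this pilot.

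Under roughly linear modification, the EDSS median split would cost about 25–36% of the information, up to about 44% if EDSS is right-skewed. The cut at 5 would cost about 35–70%. Both ranges rest on assumed distributions. The weakness of the interaction test itself, about 36% power for a 6-point difference between equal halves, follows from the plan's own SD and group sizes. It would remain a weak test after the change.

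**What to change.** Amend SAP IX.b.iv so that effect modification by EDSS and by number of non-MS medications is tested as INI × time × EDSS and INI × time × medication count, with the modifier as a continuous term. Report each slope with its confidence interval. Keep the two-group results for display, and state the observed EDSS median with them.

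The downside is the assumption of a roughly linear change in effect; if modification is a step at the cut, the split is the more efficient test. Two groups cannot check this, because two estimates always lie on a straight line. Name a check: a quadratic or spline term in the modifier, or a display in three or more groups. SAP VIII.f.i already names quadratic terms and splines for time. With 105 participants such a check will itself be rough.

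The cost is a sentence or two of SAP wording. No new data are needed, and no planned analysis is lost.
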